- Number and percentage of patients with at least one side effect
- Number and percentage of patients with at least one grade 3-4 side effect
- Number and percentage of patients with at least one SAE
- Number and percentage of patients with at least one side effect and grade 3-4 side effect due to the treatment.
- Number and percentage of patients with at least one side effect that lead to cessation of the treatment

Time to the first occurrence of grade 3-4 toxicity will be estimated by the Kaplan-Meier method.

XVII. POPULATIONS FOR ANALYSIS

The populations for the analysis are defined as follows:

Intention to treat: The intention to treat population will be composed by all included patients who were randomised to one of the two treatment groups, and patients will be analysed according to the treatment to which they were randomised. This will be the primary population for all analyses of efficacy data and baseline characteristics.

Per protocol: The per protocol population excludes patients randomised who did not receive any trial medication or who had a major violation of the protocol inclusion or exclusion criteria. Patients will be analysed according to the treatment to which they were randomised.

Safety: The safety population will include all patients who received at least one dose of trial medication. Only patients with clear documentation that no trial medication was received may be excluded. Patients will be analysed according to the treatment, which they actually received. This will be the population for the analysis of all safety data.

XVIII. ADVERSE EVENT REPORTING

1. Definition

An adverse event (AE) is defined as any untoward medical occurrence in a patient or clinical investigation subject administered a pharmaceutical product, which does not necessarily have a causal relationship with this treatment. An AE can therefore be any unfavourable and unintended sign (including an abnormal laboratory finding), symptom, or disease temporally associated with the use of a medicinal (investigational) product, whether or not related to the medicinal (investigational) product.

AE include the following:

- All suspected adverse medication reactions,
- All reactions from medication overdose, abuse, discontinuation, sensitivity, or toxicity.
- Apparently unrelated illnesses, including the worsening of a pre-existing illness.

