2.2. Definition of Severity of Adverse Events

Severity of any AE will be graded according to National Cancer Institute (NCI) Common Toxicity Criteria (CTC) version 3.0, where applicable. For each episode, the highest severity grade attained should be reported. If an AE occurs that is not listed in the CTC, the Investigator will evaluate its severity using the following criteria:

Definition of Severity of Adverse Events

Mild Grade 1 - Does not interfere with subject's usual function (awareness of symptoms or signs, but easily tolerated [acceptable]).

Moderate Grade 2 - Interferes to some extent with subject's usual function (enough discomfort to interfere with usual activity [disturbing]).

Severe Grade 3 - Interferes significantly with subject's usual function (incapacity to work or to do usual activities [unacceptable])

Life Threatening Grade 4 - Results in risk of death, organ damage, or permanent disability (unacceptable)

Note the distinction between the seriousness and the intensity of an AE. **Severe** is a measure of intensity; thus, a **severe** reaction is not necessarily a **serious** reaction. For example, a headache may be severe in intensity, but would not be classified as serious unless it met one of the criteria for serious events listed in section 3.

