5.7.3 Secondary tolerability criteria

Tolerance to treatment will be assessed by:

- chemo-embolization
- duration of sunitinib/placebo treatment, number of tablets administered, dose reductions, treatment discontinuations and their causes ;

The duration of the treatment (converted into months) will be calculated by adding the cycle durations: (cycle end date - cycle start date) + 1

- Toxicities, collected at the end of each treatment cycle, will be described according to the NCI-CTC version 4.0 criteria and their grade;
- the time to onset of grade 3-4 toxicity will be assessed;

It is defined as the time interval between the date of randomization and the date of first grade 3-4 toxicity estimated by the cycle start date + 2 weeks. Patients without Grade 3-4 toxicity at the earlier of the point or last date will be censored at the point or last date;

- The description of SAEs (analysis of pharmacovigilance)

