8.1.6 Statistics

The confidence intervals provided will be two-sided 95% confidence intervals.

Quantitative data will be described by treatment group and for the entire population, using the following descriptive statistics: number of patients, number of missing values, mean, standard deviation, median, first and third quartile, and minimum and maximum. These statistics will be considered as the usual statistics for the analysis of quantitative variables. Quantitative variables may be categorized using their median or a cut-off known from the medical literature.

Categorical variables will be summarized by treatment group and for the entire population, using the following descriptive statistics: frequencies and percentages for each level of the variable and missing values (missing values will be included in the denominator of the frequency calculation). These statistics will be considered the usual statistics for the analysis of categorical variables.

When necessary, confidence intervals for the proportions will be calculated from the exact binomial distribution.

The estimation of survival for the censored variables will be done by the Kaplan Meier method (Kaplan and Meier, 1958). This will be described by the median and rates calculated at different times. The 95% confidence intervals will

be provided. Confidence intervals for the rates will be constructed from the Greenwood variance calculated using the log-log transformation. For the median confidence interval, the upper bound will be defined as the smallest time for which the upper bound of the associated survival rate confidence interval, calculated from the Greenwood method, is less than or equal to 50%. Similarly, the lower bound will be the smallest time whose lower bound of the confidence interval of the associated survival rate is less than or equal to 50%.

The estimation of the treatment-related hazard ratios will be carried out using a stratified Cox model (Cox, 1984); the proportionality hypothesis of the rates will be tested using the graphical representation and the test based on Schöenfeld residuals (Grambsch, 1994); the linearity of the effect of the continuous variables on the risk will be assessed from the graphical representation of the martingale residuals.

Confidence intervals for the coefficient estimates of the Cox models will be calculated using the Wald method.

The median follow-up time will be calculated using the reverse Kaplan-Meier method (Shemper, 1996).

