8.6.1.3 Toxicity analysis

Toxicities will be described by treatment arm according to NCI-CTC version 4.0 criteria:

- by grade and type at the end of cycles during TACE treatment, over all cycles and during follow-up;
- Patients with at least one grade 3-4 toxicity of any type (during cycles including TACE and over all cycles), with 95% confidence interval;
- Time to Grade 3-4 toxicity will be (Toxicities collected during HEC and cycles) plotted with 95% confidence intervals and rates at different times (time to be adapted according to data) and their 95% confidence intervals.

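### The time-point rates for first grade 3-4 toxicity come from Kaplan-Meier with deaths censored, so they overstate its probability; and the plan does not say whether a fatal toxicity counts

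*SAP*

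**What the plan says.** Severe toxicity is summarised in two ways.

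- **Patient proportion.** SAP 8.6.1.3 reports "Patients with at least one grade 3-4 toxicity of any type (during cycles including TACE and over all cycles), with 95% confidence interval". Protocol XVI lists "Number and percentage of patients with at least one grade 3-4 side effect". This is a plain count over patients.
- **Time to first event.** Protocol XVI: "Time to the first occurrence of grade 3-4 toxicity will be estimated by the Kaplan-Meier method". SAP 5.7.3 runs the clock from randomization to "the date of first grade 3-4 toxicity estimated by the cycle start date + 2 weeks" and adds the censoring rule "Patients without Grade 3-4 toxicity at the earlier of the point or last date will be censored at the point or last date". SAP 8.1.6 confirms the estimator: "The estimation of survival for the censored variables will be done by the Kaplan Meier method". SAP 8.6.1.3 asks for the curve with rates at several times and their confidence intervals.

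Neither document names death as an event, a competing event or an exception for the time endpoint. Other SAP definitions do deal with death: progression-free and disease-free survival count it (5.7.2.3, 5.7.2.4), tumour control classes dead patients as uncontrolled (5.7.2.2), and the quality-of-life deterioration rule names deceased patients when it censors (5.7.4).

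On grading, Protocol XVIII 2.2 records each episode at its highest grade. Its fallback scale, for events not listed in the CTC, ends at "Life Threatening Grade 4 - Results in risk of death, organ damage, or permanent disability". No fatal grade is defined in either document.

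**The concern.** A patient who has died can no longer develop a toxicity. Kaplan-Meier treats a censored patient as still at risk after censoring. If deaths are censored, 1-KM estimates the toxicity probability in a hypothetical setting where nobody dies, and it lies above the share of patients who actually have the toxicity. Death is common here by the plan's own assumptions, and a reader will take a reported 12-month rate as patient risk.

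The grade limit raises a second question. If a site records a fatal episode above grade 4, that episode leaves no grade 3-4 record. A patient with no other grade 3-4 event would then be missing from the proportion and censored as toxicity-free on the curve. One such patient is 1/35 = 2.9 points of a phase II arm.

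**Working it through.** **1. Death rates.** Inputs: 2-year survival of 40% (placebo) and 60% (sunitinib), from Protocol XVI and SAP 5.5.3. These reproduce the plan's own figures:

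- Hazard ratio = ln(0.60)/ln(0.40) = 0.557 (SAP: 0.56).
- Deaths by Freedman's formula, two-sided 5%, 90% power: (1.960 + 1.282)² × (1.557/0.443)² ≈ 130 (plan: 130).

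With constant hazards, the monthly death hazard m is −ln(0.40)/24 = 0.0382 on placebo and −ln(0.60)/24 = 0.0213 on sunitinib. Twelve-month mortality is 1 − exp(−12m) = 36.8% and 22.5%. Twelve months is the planned treatment duration (Protocol IX).

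**2. Formulas.** For toxicity hazard l and time t:

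- Kaplan-Meier with deaths censored: 1-KM = 1 − exp(−l·t)
- Cumulative incidence: CIF = l/(l+m) × [1 − exp(−(l+m)·t)]

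**3. Excess at 12 months.** The documents give no all-type grade 3-4 rate for either arm, so I assume 20% to 90% on the 1-KM scale. Example at 40%: l = −ln(0.60)/12 = 0.0426. Placebo CIF = 0.0426/0.0807 × (1 − 0.60 × 0.632) = 32.7%. Sunitinib CIF = 0.0426/0.0639 × (1 − 0.60 × 0.775) = 35.7%.

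| 1-KM | CIF placebo | Excess | CIF sunitinib | Excess |
|---|---|---|---|---|
| 20% | 16.2% | 3.8 | 17.7% | 2.3 |
| 40% | 32.7% | 7.3 | 35.7% | 4.3 |
| 60% | 49.8% | 10.2 | 54.0% | 6.0 |
| 80% | 68.0% | 12.0 | 72.9% | 7.1 |
| 90% | 78.1% | 11.9 | 83.0% | 7.0 |

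At 24 months the same hazards give an excess of 11.6 to 21.6 points (placebo) and 7.3 to 13.3 (sunitinib).

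**4. Early toxicity.** Suppose l = 0.2 per month for three months, then zero. 1-KM = 1 − exp(−0.6) = 45.1%. CIF = 0.2/0.2382 × [1 − exp(−0.7145)] = 42.9% on placebo and 0.2/0.2213 × [1 − exp(−0.6639)] = 43.8% on sunitinib. The excess is 2.2 and 1.3 points. With the same 45.1% spread evenly over 12 months (l = 0.05), CIF is 37.0% and 40.3%, and the excess is 8.1 and 4.8 points.

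**5. Unequal toxicity.** With 20% on placebo and 60% on sunitinib, the excess is 3.8 and 6.0 points, so the order of the arms reverses. With 40% and 80% it is 7.3 and 7.1, almost equal.

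**6. Fatal toxicity.** Let f be the share of deaths without prior grade 3-4 toxicity that are themselves toxic deaths recorded above grade 4. The target is then CIF + f × D, where D = m/(l+m) × [1 − exp(−(l+m)·t)] is the probability of dying first. The 1-KM excess is cancelled when f = excess/D. At 40% toxicity on placebo, D = 29.3% and f = 7.3/29.3 = 0.25. The break-even f is about 0.11 at 20% toxicity, 0.4 at 60% and 0.6 at 80%, nearly the same in both arms. Above it, the curve understates grade 3-or-worse toxicity.

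**The case against.** The case against making much of this is strong, and most of it limits the point without removing it.

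- **Not every toxicity rate is affected.** A reader might infer that the reported toxicity rates in general are overstated. They are not. The patient proportion involves no censoring, and omitting fatal events could only lower it.
- **Fatal toxicities may not be lost.** A reader might infer that a toxic death is certain to count as no severe toxicity. The scale ending at grade 4 is only a fallback, and a fatal event coded 4 would be counted. The loss depends on a coding convention that the documents do not state. Deaths also appear as serious adverse events and in overall survival, and SAP 8.6.1.3 tabulates toxicities by grade and type.
- **No formal comparison is distorted.** SAP 8.6 describes tolerance by arm, and no test or hazard ratio is specified for this endpoint. The phase II go/no-go rule uses its own list of bleeding and liver-failure events over D0 to D7 (SAP 5.6.2, 5.7.1), without a grade limit or Kaplan-Meier.
- **The pattern between arms is not established.** Larger overstatement on placebo needs similar toxicity in both arms plus the survival gap of the phase III alternative. Under the null hypothesis mortality does not differ, and toxicity may well differ.
- **Censoring at death is inferred.** SAP 5.7.3 does not mention death. But its rule covers every patient without the event and leaves no other handling.

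What stands: the time-point rates are not patient probabilities when deaths are censored, and the event definition leaves fatal toxicity open.

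**Conclusion.** The point holds for one descriptive secondary safety curve and its time-point rates. As a measure of the probability of grade 3-4 toxicity, 1-KM is too high by about 4 to 12 points on placebo and 2 to 7 on sunitinib at 12 months. That rests on the plan's survival assumptions, constant hazards and an assumed 12-month toxicity of 20% to 90%. If about 45% toxicity falls in the first three months, the excess shrinks to about 2.2 and 1.3 points. The documents do not settle how the excess differs between arms.

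The open status of fatal toxicity is a separate gap that works the other way, and it touches both the proportion and the curve. Against true grade 3-or-worse toxicity, the net direction of the curve's error is therefore undetermined. That opposition is no reassurance, because cancellation would need a particular share of toxic deaths. The phase II primary endpoint, its decision rule and the sample size are unaffected. This is an inexpensive improvement to safety reporting, not a threat to the trial's main conclusions.

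**What to change.** In Protocol XVI and SAP 5.7.3 and 8.6.1.3:

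1. Define the event, for both the proportion and the time endpoint, as grade 3 or higher, including fatal toxicity.
2. State how deaths are handled in the time endpoint.
3. Report cumulative incidence (Aalen-Johansen), with death from other causes without prior grade 3-or-higher toxicity as the competing event. Patients alive without the event are still censored as now.

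Cost: SAP and protocol wording and a standard procedure in SAS, Stata or R. Sample size and data collection do not change. SAP 7.3 allows such adjustments before the database is frozen. The downside is that the curves are no longer plain Kaplan-Meier plots and depart from the method the protocol names, so the protocol text has to change too. A difference in cumulative incidence between arms can also partly reflect longer survival in one arm, so the curves should be read beside overall survival.

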3.2. SAE Reporting Procedure for Investigators to Sponsor

The Investigator must report all SAE, regardless of presumed causal relationship, to the Promotor by fax on a Serious Adverse Event form within 24 hours of learning of the event. Details of the relevant fax number for SAE will be provided as a separate document.

Information on Serious Adverse Events

Adverse Events (SAE) will be recorded on a specific Non Carbon Repeat (NCR) SAE form. Blank copies are included in the trial Investigator's File. The Investigator should follow up the event until resolution or stabilisation of the condition. Follow-up reports (as many as required) should be completed and faxed following the same procedure above.

A final report is required in any case once the condition is resolved or stabilised and no more information about the event is expected. The final report should be completed and faxed following the same procedure above.

4. Adverse Event Reporting Period

All AE that occur during the treatment period i.e. from the date of written informed consent to the final trial visit will be recorded in the CRF. In addition, any known untoward event that occurs subsequent to the AE reporting period that the Investigator assesses as possibly, probably or highly probably related to the Investigational Medicinal Product should also be reported as an AE.

XIX. QUALITY OF LIFE

Quality of life (QOL) will be measured by the general thirty-question EORTC quality of life questionnaire QLQ-C30. QOL is measured at baseline and every 3 months the first year (treatment period) and every 6 months the second year. Patients who withdraw will have a QOL assessment at discontinuation. These discontinuation data will be listed, but will not be included in tables or analyses. Every effort must be made to complete the QOL questionnaire. Where a whole questionnaire has not been completed but the patient has survived to the appropriate time, one of the following options will be recorded on the CRF.

- 1 = patient felt too ill
- 2 = clinician or nurse felt the patient was too ill
- 3 = patient felt it was inconvenient, takes too much time
- 4 = patient felt it was a violation of privacy
- 5 = patient didn't understand the actual language/ illiterate
- 6 = administrative failure to distribute the questionnaire to the patient
- 7 = other, please specify

For codes 1 or 2, data will be regarded as 'missing too ill' whereas for any of the other

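### The time-to-grade 3-4 toxicity curve counts events only from TACE and drug cycles but keeps patients at risk to the last date, so a first toxicity on a follow-up record is plotted as toxicity-free

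*SAP*

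**What the plan says.** - **Time at risk.** SAP 5.7.3 starts the clock at randomization and ends it, for patients without an event, as follows: "Patients without Grade 3-4 toxicity at the earlier of the point or last date will be censored at the point or last date". The last date is not defined there. By analogy with SAP 5.7.4 and 8.1.2 I read it as the date of last news, normally the date on the monitoring form.
- **Event date.** The same section uses the "date of first grade 3-4 toxicity estimated by the cycle start date + 2 weeks".
- **Event source.** SAP 5.7.3 refers to "Toxicities, collected at the end of each treatment cycle". SAP 8.6.1.3 describes the curve's source as "Toxicities collected during HEC and cycles". I read HEC as chemoembolization (TACE).
- **Follow-up toxicity.** The tables in SAP 8.6.1.3 go further than the curve: toxicities are described "by grade and type at the end of cycles during TACE treatment, over all cycles and during follow-up". In the protocol's section on the adverse event reporting period, events "from the date of written informed consent to the final trial visit will be recorded in the CRF".
- **Durations.** Protocol IX plans one year of drug (8 cycles), ending earlier on relapse or progression. SAP 5.5.3 allows 3 years of follow-up after the last inclusion.
- **Estimator.** Protocol XVI specifies Kaplan-Meier. Neither document says how death or stopping drug is handled in this analysis.

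**The concern.** The window in which an event can be counted does not match the window in which a patient is at risk. After the last cycle a patient stays in the denominator but cannot enter the numerator.

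This has two consequences. First, the endpoint is defined as the first grade 3-4 toxicity, without restriction, yet a patient whose first one appears on a follow-up record is drawn as never having had one. The data exist and are left out. Second, the curve flattens as patients leave drug. Two arms with the same risk while on drug will show different curves if one stops sooner, and the arm that stops sooner looks safer.

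This curve is the plan's time-to-event summary of grade 3-4 toxicity, in a trial whose phase II step is there mainly to assess the safety of the combination.

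**Working it through.** **Step 1: set the rules side by side.**

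| Element | Rule | Covers follow-up records? |
|---|---|---|
| Endpoint (SAP 5.7.3) | first grade 3-4 toxicity after randomization | yes, no restriction |
| Event source (SAP 8.6.1.3) | TACE and cycles | no |
| Event date (SAP 5.7.3) | cycle start + 2 weeks | no, there is no cycle to date from |
| End of risk (SAP 5.7.3) | point date or last date | yes, risk runs through follow-up |
| Toxicity tables (SAP 8.6.1.3) | cycles with TACE, all cycles, follow-up | yes |

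A patient with a first grade 3-4 toxicity at, say, month 15 meets the definition and appears in the follow-up table. The same patient is censored without an event in the curve.

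Progression-free survival is handled differently. SAP 5.7.2.3 censors at the last informative examination, and uses last news if a surveillance sheet documents no progression. The toxicity rule has no such link to assessment.

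**Step 2: size.** The plan gives no rate for this endpoint, so there is no figure to reproduce, and the inputs below are assumptions. Let λ be the toxicity hazard on drug and μ the hazard of stopping drug, both constant and independent. No event can be counted after stopping.

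- Curve as the SAP writes it: F(t) = λ/(λ+μ) × [1 − exp(−(λ+μ)t)]
- Hypothetical rate if nobody stopped (censoring at stop): G(t) = 1 − exp(−λt)

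Worked case, 50% toxicity and 50% stopping by 12 months: λ = μ = −ln(0.5)/12. Then F(12) = 0.5 × (1 − 0.25) = 37.5%, and G(12) = 50%.

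12-month values of F over the assumed grid:

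| G(12) | 30% stop early | 50% stop early | 70% stop early |
|---|---|---|---|
| 30% | 25.5% | 22.1% | 18.1% |
| 50% | 42.9% | 37.5% | 31.1% |
| 70% | 60.9% | 53.9% | 45.5% |

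The smallest and largest gaps lie on the diagonal. There λ = μ, so the gap reduces to G(t)²/2:

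- 12 months: 0.30²/2 = 4.5 points to 0.70²/2 = 24.5 points.
- 6 months: 0.1633²/2 = 1.3 points to 0.4523²/2 = 10.2 points.
- 3 months: 0.0853²/2 = 0.4 points to 0.2599²/2 = 3.4 points.

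A simulation of 400,000 patients added deaths (from 40% two-year survival, SAP 5.5.3), a 12-month cap on drug, and assumed follow-up of 4-13 months (phase II) or 36-60 months (phase III). The gaps changed by no more than about 0.5 point.

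**Step 3: comparability of arms.** Take two arms with the same 50% on-drug risk, one with 30% and the other with 70% stopping early. Their curves read 42.9% and 31.1% at 12 months, 11.8 points apart, with no difference in on-drug risk.

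**Step 4: a different target.** F is itself the cumulative incidence of on-treatment toxicity when death is set aside. With death as a competing event (hazard δ = −ln(0.4)/24), the 50%/50% case gives λ/(λ+μ+δ) × [1 − exp(−12(λ+μ+δ))] = 0.3758 × 0.8419 = 31.6%. The SAP curve, which in effect censors deaths, gives 37.5% and is now too high by about 6 points. The simulation gave 31.7% and 37.6%.

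**The case against.** The strongest reply concerns the target. A reader might infer that the SAP curve understates toxicity in general, for example by reporting 37.5% when the truth is 50%. The documents do not support that. If no grade 3-4 toxicity occurs off drug, and deaths are set aside, 37.5% is the proportion of patients who actually had one; 50% is what would have happened had nobody stopped. The plan nowhere names that hypothetical as its target. Against cumulative incidence with death as a competing event, the curve is too high. This part of the objection stands, and the direction of any error depends on the target.

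A reader might also infer that time after drug is unobserved. It is not: follow-up toxicities are tabulated, and adverse events are recorded to the final visit. The time is observed but not counted in this curve.

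Further points that stand:

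- The parenthesis in SAP 8.6.1.3 may have been meant to add TACE forms to the cycle-end forms, not to exclude follow-up. Even so, the dating rule has no date for a follow-up toxicity.
- Equating the last date with last news is an inference.
- The illustration treats stopping as independent of toxicity. Patients who stop because of grade 3-4 toxicity already have the event and add no event-free time off drug, and censoring at drug stop could itself be informative.
- The phase II cut-off is one week after the last patient's last TACE (SAP 7.2.2), so few patients would then have reached 12 months. SAP 8.6.1.3 also lets the time points adapt to the data.
- Protocol XI continues clinical and laboratory visits after drug. If toxicity is assessed there, censoring at the last toxicity assessment will fall close to last news. The fix then recovers omitted events but does not lift the curve to the hypothetical rate.

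None of this removes the mismatch: recorded events that meet the definition are left out of the curve.

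**Conclusion.** The point holds in limited form. As written, the event window (TACE and cycles) and the risk window (to the point date or last date) do not match, and a first grade 3-4 toxicity on a follow-up record is plotted as no toxicity. Arms with different time on drug cannot be compared on this curve as a measure of risk.

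The documents do not determine the size. The loss is nil if no first grade 3-4 toxicity occurs after the last cycle and the curve is read as cumulative on-treatment incidence with deaths censored. Against the hypothetical rate without stopping, the shortfall is 0.4-3.4 points at 3 months and 4.5-24.5 at 12 months, on assumed toxicity and early-stopping rates of 30-70% each. A general claim that the plan understates toxicity is not supported.

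The curve is secondary and descriptive, and the SAP specifies no test on it. The phase II go/no-go count, the overall survival test and the simple percentage with at least one grade 3-4 toxicity do not depend on this censoring rule.

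**What to change.** In SAP 5.7.3 and 8.6.1.3:

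1. Count the first grade 3-4 toxicity on any toxicity record: TACE, cycle or follow-up.
2. Keep the cycle-based date for toxicities within a cycle. For those outside a cycle, use the recorded date or the assessment date.
3. Censor patients without an event at their last toxicity assessment, and state how death is handled.

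If the sponsor prefers an on-treatment curve, label it so and report it as a cumulative incidence with treatment stop and death as competing events.

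The cost is SAP wording and slightly more programming on data already collected. Under the first option, reported rates may be somewhat less favourable.
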